Agriculture is a major economic activity in Guatemala, with 70% of families working in this sector. Family agriculture has many obstacles, including lack of access to land and the expansion of cash crop (e.g., sugar cane, African palm) plantations. Most of the food that is grown locally is exported, rather than being used for local consumption.

Public and private organizations in Guatemala have worked to promote the production of food for consumption. However, very few of them have measured the impact of agricultural initiatives on nutritional status. Moreover, this is the first study in North Tecpán to evaluate the potential impact that adding a home food production (for

PROTOCOL TITLE:

Evaluating a family-based nutrition and garden intervention in rural Guatemala

consumption) component to a health-oriented nutrition program can have on maternal and child diet quality and nutritional status and household food security.

3. Study Design

This is a quasi-experimental study with an intervention group and a nonrandomly selected control (standard care) group.

- The *standard-of-care group* will consist of subjects recruited from Maya Health Alliance's nutrition program in prioritized communities of *North Tecpán, Chimaltenango, Guatemala*. Subjects in the standard care group will receive the current standard child nutrition care (growth monitoring, deworming medication, micronutrient supplementation, nutrition education classes and home visits).
- The *intervention group* will consist of subjects recruited from MHA's nutrition program in prioritized communities of *San Andrés Semetabaj, Sololá, Guatemala*. Subjects in the intervention group will receive the standard child nutrition care plus an additional agriculture component (agriculture education classes, supplies to build a home garden near the family home and on-going agricultural support).

A quasi-experimental design was selected because it was determined that household level randomization would be culturally and logistically difficult.

Both sites are rural. The intervention and control communities are 90 minutes apart by car and have similar prevalence of chronic malnutrition in children and similar sociodemographic characteristics (education levels, economic activity, health services, school access and food access).

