In addition to the primary study endpoints (defined below), we will use the RE-AIM framework (Glasgow 1999) to evaluate the implementation of the intervention at the caregiver, provider and community levels. Broadly, the five elements of RE-AIM are: reach, effectiveness, adoption, implementation and maintenance. For each element, a variety of factors affecting implementation will be assessed. A select number of constructs from the Consolidated Framework for Implementation Research (CFIR) (Damschroder 2013) will also be considered as implementation factors within the RE-AIM framework. Data for this implementation analysis will be gathered through program documentation and auditing, home visit surveys, focus groups with participants, key informant interviews and semi-structured community interviews. More details about the RE-AIM framework for this study, the implementation factors to be assessed and the instruments for assessing them are outlined in Appendix J.

4. Inclusion and Exclusion Criteria

The study involves enrollment of subjects into an add-on gardening intervention who are already participating in an intensive standard-of-care nutrition intervention by MHA staff. Therefore, clinical staff (community health workers) at MHA who run that nutrition intervention will ascertain initial interest in participation in this study from their clients enrolled in the nutrition intervention. Subjects will be approached in their homes to discuss potential participation in the study.

PROTOCOL TITLE:

Evaluating a family-based nutrition and garden intervention in rural Guatemala

If clients express initial interest, the community health worker will provide that family's contact information to a study nurse, who is trained in human subject's research ethics and is a native speaker of Kaqchikel, the language spoken by the majority of the potential research subjects. This nurse will then conduct a home visit to potential subjects to explain the proposed research activities in more detail. If the family agrees to participate, then the nurse will administer the consent process and enroll them in the study.

Inclusion criteria are:

- Children who are already scheduled to be enrolled in MHA's intensive home-based nutrition program (non-investigational, standard of care) who are 6-24 months of age at the time of enrollment with a height-for-age Z scores of ≤ -2 – Households of children with height-for-age Z scores of ≤ -2.5 will be prioritized.

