- The add-on agricultural/garden intervention (received by the intervention group only) will last 8 months and will include monthly agricultural classes and monthly home visits. The agricultural/garden intervention will involve approximately 16 hours of contact with MHA agricultural personnel, in addition to the time dedicated to the standard nutrition intervention.

A select number of participants (approximately 10) in the *intervention group* only will be asked to participate in one of two focus groups, approximately 90 minutes in length, between 6 and 9 months after the first enrollment. Participation in the focus groups will be fully voluntary and will not have any impact on the services or benefits received by the participants.

A small number of community leaders and Wuqu' Kawoq staff will be asked to participate in interviews, approximately 90 minutes in length, between 6 and 9 months after the first enrollment. Participation in the interviews will be fully voluntary.

The expected total duration of the study is approximately 3 years from the date of IRB approval.

7. Study Endpoints

The primary endpoints of this study are changes in the prevalence of:

- *Adequate diet quality*, as assessed by the World Health Organization (WHO) Infant and Young Child Feeding Indicators (IYCFI) (WHO, 2007) minimum dietary diversity, minimum meal frequency, minimum acceptable diet) for children and the Minimum Dietary Diversity for Women (MDD-W) indicator for caregivers. (FAO 2016)
- *Household food insecurity*, as assessed by the Global Food Insecurity Experience Scale (household referenced) (FAO 2017)

Secondary endpoints of the study include changes in: child length-for-age Z-score; child weight-for-age Z-score; child weight-for-length Z-score; child prevalence of stunting, wasting and underweight; and household total crop species diversity.

PROTOCOL TITLE:

Evaluating a family-based nutrition and garden intervention in rural Guatemala

This study involved no more than minimal risk, so no safety endpoints are specified.

8. Research Setting

The study will be conducted in prioritized communities of North Tecpán, Chimaltenango and San Andrés Semetabaj, Sololá (see additional details in **Section 3. Study Design**). These are rural Mayan language speaking communities where MHA has been working providing primary care and nutrition services for several years. MHA collaborates closely with multiple other NGOs as well as Ministry of Health staff in the region.

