- Monthly home visits from a study agronomist to provide assistance to build a garden near the family home and on-going support throughout the study

PROTOCOL TITLE:

Evaluating a family-based nutrition and garden intervention in rural Guatemala

Study data will be independently collected by a study nurse for all enrolled subjects at 0, 6, 12 and 18 months:

- Basic health history and demographics Appendix A
- Child weight and length/height Appendix B
- Household Quick Poverty Score (QPS) Appendix C
- Food Insecurity Experience Scale (household) Appendix D
- WHO Infant and Young Child Feeding indicators (child) Appendix E
- MDD-W Indicators (caregiver) Appendix F
- Agriculture Inventory Survey (household) to measure crop diversity and crop utilization Appendix G

Note that child weight and length and WHO IYCFI are already routinely collected as part of evaluation data for the standard-of-care nutrition services.

Additional data will be collected by the study agronomist for the *intervention group only* during the first agricultural home visit and at one additional agricultural home visit approximately 4 months thereafter:

- Agricultural Home Visit Baseline Survey (Baseline Agricultural Practices; Gardening Experience and Motivation) Appendix H
- Agricultural Home Visit Follow-up Survey (Adoption of Methods; Level of Home Garden Maintenance; Hours Worked in Home Garden) Appendix I

13. Data Analysis

Descriptive statistics for each group will be calculated using Stata (StataCorp, College Station, Texas). Family poverty scores will be calculated with a validated numerical scoring system commonly used in Guatemala. Changes in primary and secondary study outcomes will be compared between study groups using the chi-square test, paired t-tests (or the non-parametric equivalent) and linear and logistic regression as appropriate.

Within the intervention group, the rate of overall adoption will be compared descriptively across various demographic groups, and changes in primary and secondary outcomes will also be compared descriptively between adopters and non-adopters. Focus groups and interviews will be coded and analyzed thematically using select constructs from the Consolidated Framework for Implementation Research (CFIR) as a framework.

This is a pilot study to determine the feasibility of a garden intervention and to generate an initial effect size estimate for future, well-controlled studies. As such no formal power analysis will be performed.

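### Gardening experience and baseline practices are recorded only in the garden group, so self-selection on them cannot be compared or adjusted for; asking the factual items of all 140 families at month 0 is a cheap improvement.

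*Combined protocol and SAP*

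**What the plan says.** Section 3 describes the design: "This is a quasi-experimental study with an intervention group and a nonrandomly selected control (standard care) group". Arm and site coincide, with San Andrés Semetabaj as the intervention site and North Tecpán as the control site. Section 6 confines the garden to one arm: "The add-on agricultural/garden intervention (received by the intervention group only) will last 8 months".

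Under Section 4, community health workers "will ascertain initial interest in participation in this study from their clients enrolled in the nutrition intervention". Interested families are passed to the study nurse: "This nurse will then conduct a home visit to potential subjects to explain the proposed research activities in more detail". Consent follows that visit. Section 20 describes the same sequence. The eligibility lists contain nothing on land, water or willingness to garden, although Section 2 notes: "Family agriculture has many obstacles, including lack of access to land".

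Section 12 sets out two streams of data:

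- **Both groups:** "Study data will be independently collected by a study nurse for all enrolled subjects at 0, 6, 12 and 18 months". The list covers health history and demographics, anthropometry, the Quick Poverty Score, food insecurity, child and caregiver diet, and an Agriculture Inventory Survey on crop diversity and use (Appendix G).
- **Garden group:** "Additional data will be collected by the study agronomist for the *intervention group only* during the first agricultural home visit", with a second visit about four months later. The first of these surveys is the "Agricultural Home Visit Baseline Survey (Baseline Agricultural Practices; Gardening Experience and Motivation) Appendix H".

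Section 13 compares changes between groups with simple tests and with linear or logistic regression where appropriate. It names no covariates. It also states that the pilot is meant to yield a first effect size for later studies.

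**The concern.** Enrolling means something different at each site. Section 29 says that families receive the standard nutrition and primary care services whether or not they take part, and Section 23 says that nobody is paid. In North Tecpán, joining therefore adds essentially data collection. In San Andrés Semetabaj it adds classes, supplies that the family keeps, and monthly agronomist visits, at about 16 hours of contact. A family with no usable space or no interest in growing food has a reason to decline at the garden site that it does not have at the control site.

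Section 3 argues that the two sets of communities are alike in malnutrition, education, economy and food access. That does not address which families within each community agree to join. Selection produced by the offer could occur even if the two municipalities were identical.

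If such selection occurs, and if families able and inclined to garden would have improved faster anyway, the difference is counted as a garden effect. It then passes into the effect size handed to the next study.

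**Working it through.** The documents give no figure for this selection and no power calculation, so there is no stated number to reproduce. The check has two parts.

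**1. Which relevant factors are measured in whom**

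| Factor | Garden group | Control group |
|---|---|---|
| Crop diversity and use (Appendix G) | month 0 | month 0 |
| Quick Poverty Score, demographics | month 0 | month 0 |
| Baseline diet and food insecurity | month 0 | month 0 |
| Baseline agricultural practices (Appendix H) | first agricultural visit | not listed |
| Gardening experience and motivation (Appendix H) | first agricultural visit | not listed |
| Usable space, water for a garden | no item described | no item described |
| Refusals and reasons by site | none described | none described |

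A covariate observed in one arm only cannot be compared between arms or entered in a between-group model. Appendix H can therefore support only descriptions within the garden group. The first three rows are available in both arms, and they cover part of the ability to garden. Comparing changes also removes stable differences in outcome level. It does not remove a difference in trajectory linked to experience or motivation.

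**2. Scale, on assumed inputs**

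Let Δ be the difference between sites in the share of families able and keen to garden (garden site minus control site). Let g be the extra improvement of such families on a binary diet indicator, whatever the garden does. Then

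bias = Δ × g.

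- Lower end: Δ = 10 points, g = 10 points: 0.10 × 0.10 = 0.01, or 1 point.
- Middle: Δ = 20 points, g = 20 points: 0.20 × 0.20 = 0.04, or 4 points.
- Higher: Δ = 30 points, g = 30 points: 0.30 × 0.30 = 0.09, or 9 points.
- Upper end: Δ = 40 points, g = 30 points: 0.40 × 0.30 = 0.12, or 12 points.

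If Δ or g has the opposite sign, so does the bias. Neither is given in the documents.

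Two yardsticks:

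- **The earlier randomised trial of the nutrition programme (Section 2)** reports a risk difference of 16.9 points for minimum dietary diversity. 1/16.9 = 0.06 and 12/16.9 = 0.71.
- **Sampling error** with 70 per group and a proportion of 0.5: SE = √(2 × 0.5 × 0.5 / 70) = 0.0845, so the 95% half-width is 1.96 × 0.0845 = 0.166, or 16.6 points.

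With no true effect, the chance of a two-sided 5% rejection is 1 − Φ(1.96 − bias/SE) + Φ(−1.96 − bias/SE):

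| Bias (points) | Rejection rate |
|---|---|
| 1 | 5.2% |
| 4 | 7.6% |
| 9 | 18.7% |
| 12 | 29.5% |

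These rates treat the outcome as a simple difference of two proportions and ignore dropout and clustering.

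**The case against.** **The selection is not wholly invisible.** A reader might infer that self-selection toward families able and keen to garden can be neither seen nor removed. The documents do not support that. The month-0 Agriculture Inventory shows what each household already grows, and it is taken in both groups together with poverty score, demographics and baseline outcomes. Regression is allowed. This objection stands. What is left is experience, baseline practices and motivation, plus the absence of any commitment to use the proxies.

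**Enrichment and its direction are not shown.** A reader might also infer that the garden group is enriched and the effect therefore inflated. Section 2 lists land among several obstacles to family agriculture in general, whereas the intervention is a garden near the home with free supplies and help. Section 13 expects non-adopters within the garden group. Free supplies could draw in more food-insecure families, and controls who accept four research visits without payment may be unusually engaged. Either could offset or reverse the bias. This stands too.

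**Unseen appendices may already help.** Appendices A, G, H and J are not in the supplied text. Appendix G might record growing space, and the RE-AIM reach element (Section 4, Appendix J) might record refusals. This cannot be checked here, so the request for a refusal log is conditional.

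**Asking controls about motivation has its own problems.** Garden-site answers would already be shaped by the offer, and control answers would be hypothetical, so the variable would not mean the same thing in both arms. Section 18 names conflict between communities as a risk if families learn that others receive gardens, and asking controls whether they would accept one could raise it. This stands and limits the fix to factual items.

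**It is a pilot with a declared non-random design.** That lowers the stakes but does not remove them, because Section 13 makes an effect size estimate one of the study's products.

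**Conclusion.** The point holds as a cheap improvement. Consent follows different offers at the two sites, and the items on practices, gardening experience and motivation exist in one arm only. Differential self-selection on them cannot be compared or adjusted for as planned. The data taken in both groups are partial proxies, and no adjustment set is named.

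The bias plausibly favours the garden, but its direction and size are unknown from the documents. The 1 to 12 points are an illustration on assumed inputs with an assumed sign; they are not an estimate of the bias in this study. Even the upper end lies inside the 16.6-point half-width, so the main harm would be a shifted effect size for the next study.

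The conclusion assumes that the nurse's explanation before consent tells garden-site families about the garden, which the order of steps in Sections 4 and 20 implies. It also assumes that the unseen appendices contain no equivalent items for controls. No household covariate can separate arm from site, so the change reduces confounding without making the contrast causal.

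**What to change.** 1. At the month-0 visit, before any agricultural contact, have the study nurse ask all 140 families the factual Appendix H items (baseline agricultural practices, prior gardening experience). Add two items, usable space near the home and access to water. Use the same words at both sites.
2. In Section 13, name these items, the month-0 crop inventory, the poverty score and the baseline value of the outcome as covariates in the between-group regression. Report the unadjusted comparison beside it.
3. Record the number of families approached and the reasons for refusal by site, unless the RE-AIM reach element in Appendix J already does so.
4. Leave the motivation items in the garden group for the within-group description of adoption. Do not adjust for motivation, do not ask controls whether they would accept a garden, and do not run an analysis restricted on that answer.

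The cost is a few more minutes per family at a visit that already takes place, with no new staff. The questions could slightly prompt gardening among controls, which the repeated Agriculture Inventory would show. The covariates should be coded simply. If minimum acceptable diet were at the 15% to 21% seen in the 50-child pilot (Section 2), 140 children would give only about 21 to 29 positives (0.15 × 140 = 21; 0.21 × 140 = 29.4), which limits how many terms a logistic model can carry. Residual confounding by site remains.

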The specific aims of this pilot project are:

1) To evaluate the feasibility of studying whether implementation of family gardens paired with a nutrition intervention program in rural Guatemala will lead to improvements in maternal and child dietary diversity, child growth and household food insecurity compared to a nutrition intervention program alone.

2) Evaluate the implementation of the intervention through the Reach Effectiveness Adoption Implementation Maintenance (RE-AIM) framework.

We hypothesize that by augmenting a standard nutrition intervention with improved household food access through a garden intervention, child growth, dietary diversity and food security will improve compared to outcomes with the nutrition intervention alone.

2. Background

Children in Guatemala are at high nutritional risk, with a 47% prevalence of stunting (chronic malnutrition) and low full coverage with vitamin A supplements (UNICEF 2016). Only half of Guatemalan children receive a minimum acceptable diet (according to World Health Organization criteria measuring dietary diversity and meal frequency) from 6-23 months (UNICEF 2016). The indigenous Mayan population is disproportionately affected by poverty, food insecurity and malnutrition, with the prevalence of chronic malnutrition reaching as high as 70% in rural areas.

Wuqu' Kawoq/Maya Health Alliance (MHA) has conducted several studies to determine what nutrition interventions really work to prevent and treat chronic malnutrition. As a result of these studies, MHA established a home-based nutrition program whose goal is catch-up growth, improvement of minimum dietary diversity, minimum meal frequency, and minimum acceptable diet and increased caregiver knowledge. In a 50-child pilot, this intervention resulted in a mean change in height for age Z score (HAZ) from -3.67 ± 0.99 to -3.37 ± 0.89 over 6 months and an increase from 15-21% on minimum acceptable diet. In a subsequent RCT of this intervention, a trend toward improved growth at 6 months was observed, although the change was not statistically significant. However, minimum dietary diversity and minimum acceptable diet both improved significantly (risk difference 16.9 and 15.9%, respectively). The intervention also resulted in improved daily intake of legumes, eggs, and vitamin A rich fruits and vegetables (risk difference 16.5, 10.4, 12.7% respectively) (Martinez et al, 2018).

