- At least one caregiver willing to provide written informed consent
- Caregiver of a child enrolled in the study, including women who may be pregnant
- Planned residence in the study area for the next 18 months

Exclusion criteria are:

- Children with acute malnutrition (weight for length Z scores of ≤ -2.0)
- Children with a severe medical illness that affects growth (e.g., heart disease, kidney disease, genetic condition) as determined by a MHA/Wuqu' Kawoq staff physician.
- Caregivers with cognitive impairments that prevent them from being able to provide informed consent

Children who are ineligible for enrollment in the research study will receive standard care (the home-based nutrition intervention) from MHA.

5. Number of Subjects

The study will enroll 140 children and their primary caregivers into two study groups: standard-of-care (n=70 children and 70 caregivers) and intervention (n=70 children and 70 caregivers).

6. Study Timelines

Five to ten families per month will be enrolled into the study from each study community. We anticipate that recruitment will take ~7-14 months.

The research team will have contact with enrolled participants over the course of 18 months. The primary study data collection time points will be at 0 months (enrollment), 6 months (end of standard of care/nutrition intervention), 12 months, and 18 months. It is anticipated that each of these study data collection visits will last approximately 1 hour,

PROTOCOL TITLE:

Evaluating a family-based nutrition and garden intervention in rural Guatemala

for a total of 4 hours. In addition to that, for the *intervention group only*, data will be collected at the first monthly agricultural home visit and at one additional agricultural home visit approximately 4 months thereafter. Each of these agricultural home visits will last approximately 1 hour for a total of an additional 2 hours. Combined, the total data collection time for the participant in the *intervention* group will be 6 hours.

The duration of the study interactions with the children and their caregivers is as follows:

- Standard child nutrition care (received by both groups) will last 6 months and will include nutrition classes for 5 weeks and one home visit a month. Standard nutrition care will involve approximately 16 hours of contact with MHA clinical personnel.

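### Section 13 lists paired t-tests for comparing change between two unmatched groups; a paired test cannot give the garden effect on the continuous secondary outcomes

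*Combined protocol and SAP*

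**What the plan says.** Section 13 (Data Analysis) states one aim and gives one list of methods. Changes in the primary and secondary outcomes are to be "compared between study groups using the chi-square test, paired t-tests (or the non-parametric equivalent) and linear and logistic regression as appropriate". The same section says the pilot is also meant "to generate an initial effect size estimate for future, well-controlled studies", and it waives a formal power analysis.

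Section 3 (Study Design) describes the groups: "This is a quasi-experimental study with an intervention group and a nonrandomly selected control (standard care) group". Standard-care families come from North Tecpán and garden families from San Andrés Semetabaj, 90 minutes away by car. Sections 3 and 12 give both groups the same child nutrition services, and the garden group receives the agricultural component on top. Neither section describes matching families across the two areas.

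Section 7 (Study Endpoints) defines the primary endpoints as changes in prevalence. The continuous outcomes are secondary: "Secondary endpoints of the study include changes in: child length-for-age Z-score; child weight-for-age Z-score; child weight-for-length Z-score", together with household crop species diversity.

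**The concern.** The stated aim, comparing change between groups, is the right one. The difficulty is that one of the methods named for it cannot do it. A paired test needs pairs. The only pairs in this study are two visits by the same child or household, so the test assesses whether one group changed. It does not use the other group at all. The phrase in parentheses does not help, because the non-parametric counterpart of a paired t-test is also a within-group test. The sentence lists no two-sample t-test or rank-sum test.

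This matters because the garden effect is the garden group's change minus the standard-care group's change. Change within the garden group alone mixes the nutrition programme, the child's growing older and the garden. If a paired result on a Z-score were taken as the effect size, the next study could be planned on an effect that belongs partly or wholly to care that both groups received.

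**Working it through.** The plan gives no power, alpha or effect-size figure on this point, so there is nothing of its own to reproduce. The check is an illustration on HAZ: what does each test return when the garden has no effect?

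**Inputs from the documents**
- 70 children per group (Section 5).
- A "mean change in height for age Z score (HAZ) from -3.67 ± 0.99 to -3.37 ± 0.89 over 6 months" in the earlier 50-child pilot (Section 2). The gain is −3.37 − (−3.67) = 0.30, with SDs of 0.99 before and 0.89 after.

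**Assumptions not in the documents**
- Within-child correlation r between the two visits of 0.5 to 0.9.
- The same true gain in both groups, so the garden effect is 0.
- A two-sided 5% level, no dropout and no correlation within communities.
- A smaller gain of 0.15 as a sensitivity case.

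**Formulas**
- SD of change = √(0.99² + 0.89² − 2r × 0.99 × 0.89). At r = 0.5 this is √(1.7722 − 0.8811) = 0.944. At r = 0.9 it is √(1.7722 − 1.5860) = 0.4315.
- Chance that the garden group's paired t-test is significant: noncentral t with 69 df and noncentrality gain × √70 / SD. For a gain of 0.30 and r = 0.5, the noncentrality is 0.30 × 8.367 / 0.944 = 2.66.
- Standardised within-group change = gain / SD of change.
- 95% half-width of the between-group difference in change = t(138 df) × SD × √(2/70) = 1.977 × 0.169 × SD.

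| r | SD of change | Paired test significant, gain 0.30 | Standardised change, gain 0.30 | Paired test significant, gain 0.15 | Half-width of between-group difference |
|---|---|---|---|---|---|
| 0.5 | 0.944 | 74.6% | 0.318 | 25.9% | 0.316 |
| 0.6 | 0.846 | 83.3% | 0.355 | 31.0% | 0.283 |
| 0.7 | 0.734 | 92.1% | 0.409 | 39.2% | 0.245 |
| 0.8 | 0.602 | 98.4% | 0.498 | 53.8% | 0.201 |
| 0.9 | 0.432 | >99.9% | 0.695 | 81.8% | 0.144 |

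**The valid comparison.** Under the same conditions a two-sample t-test on the change scores is significant in 5.0% of studies at both r = 0.5 and r = 0.9 (100,000 simulations). That is 2.5% in favour of the garden group.

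**Paired tests run in both groups and compared by eye.** The chance that only the garden group is significant is power × (1 − power). At r = 0.5 and a gain of 0.30 this is 0.746 × 0.254 = 0.19. Over r = 0.5 to 0.9, simulation gives 0% to 19% for a gain of 0.30 and 15% to 25% for a gain of 0.15. These figures also depend on the common gain and not on any garden effect.

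**The case against.** The strongest reply is that valid methods stand in the same sentence. Linear regression of change on group is equivalent to the two-sample t-test, and the list ends by leaving the choice to what is appropriate. The paired tests may have been meant for within-group change and folded into one sentence. Nothing in Section 13 says that a paired result will be reported as the garden effect. All of this stands, and it limits the point to a wrong entry in the list. It does not remove it: the sentence gives the paired test a between-group role, and nothing in the supplied text corrects that.

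The illustration also rests on thin ground. The correlations and the 0.15 gain are assumed. The 0.30 gain is uncontrolled and comes from children with a mean HAZ of −3.67, whereas Section 4 admits children at −2 or below. In the later randomised trial of the nutrition programme, Section 2 reports that "a trend toward improved growth at 6 months was observed, although the change was not statistically significant". The figures show a mechanism and do not forecast this study.

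A reader might infer three stronger claims.
- *That the primary endpoints are affected.* They are not. They are prevalences, and chi-square and logistic regression are listed and can compare independent groups.
- *That 75% to 100% is the study's false-positive rate.* It is not. It is the power to detect a real within-group change, and becomes an error only if that change is attributed to the garden.
- *That leaving the analysis visit unnamed is part of the error.* The visits are "6 months (end of standard of care/nutrition intervention), 12 months, and 18 months", and Section 6 also says "The add-on agricultural/garden intervention (received by the intervention group only) will last 8 months", so month 6 falls before the garden component ends. Naming a visit is therefore advisable. But an unnamed visit is missing detail, whereas the paired-test entry is wrong as written.

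**Conclusion.** The point holds for the continuous secondary outcomes. A method that Section 13 names for comparing change between groups cannot make that comparison in unmatched groups, and so cannot be the source of the pilot's effect size on those outcomes.

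On the assumptions above, with a common HAZ gain of 0.30 and no garden effect, the garden group's paired test would be significant in 75% to 100% of studies, against 5% for a two-sample test of change. The paired analysis would show a standardised change of 0.32 to 0.70 where the garden effect is 0. With a common gain of 0.15 the paired test would be significant in 26% to 82%. The wording fault itself depends on none of these assumptions. The practical harm depends on someone using the paired result as the garden effect, which the plan does not say it will do.

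**What to change.** In Section 13, replace the paired t-test entry and its non-parametric alternative with: *two-sample t-tests of change from baseline (or the rank-sum test), or linear regression of change on group, reported as the between-group difference with a 95% CI*. Then add: *Paired tests describe change within each group only and are not the source of the effect size.* It would be sensible to name the analysis visit at the same time, as a clarification.

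The cost is a short rewording. No new data are needed, and Stata is already named. The price is that the imprecision becomes visible: about ±0.14 to ±0.32 HAZ with 70 per group under the assumed correlations. Section 3 refers to several communities in each area without giving a number, so with correlation inside communities the true intervals would be wider. The correction also leaves the design as it is: with each group drawn from its own area, the estimate cannot separate the garden from other differences between the two places, and the report should say so.
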